#### 5.5.12. Change in Clinical Management Plan from Questionnaire

A change in the Clinical Management plan from the pre-PyL scan assessment to the post-PyL scan assessment will be defined from any of the following questions:

- If there is a change in planned diagnostic biopsy from pre-PyL to post-PyL
- If there is a change in planned surgery from pre-PyL to post-PyL
- If type of surgery planned pre-PyL does not match post-PyL
- If type of planned chemotherapy changes from pre-PyL to post-PyL
- If there is a change in planned other immunotherapy/investigational therapy from pre-PyL to post-PyL
- If planned radiation therapy changed from pre-PyL to post-PyL
- If chemotherapy plan changed from pre-PyL to post-PyL
- If hormonal/ADT plan changed from pre-PyL to post-PyL
- If there is a change in other therapy/intervention from pre-PyL to post-PyL

An overall change score will be calculated as well as a change in each of the above criteria alone.

#### **5.5.13. PSA groups**

PSA will be categorized into the following groups:

<0.2 ng/mL
0.2 to <4.0 ng/mL
4 to <20.0 ng/mL
20.0 to <50.0
ng/mL
≥50 ng/mL

#### 5.5.14. Gleason Scores

The Gleason score will be derived by concatenating the primary Gleason grade to the secondary Gleason grade, separated by a plus sign (e.g., 3+4). The total Gleason score will be computed as the sum of the primary and secondary Gleason grades (7 in the example of 3+4 provided here).

Gleason Score from prostatectomy will be categorized into the following groups as shown in the table based on the sum of primary and secondary Gleason Grades:

Primary Gleason Grade	Secondary Gleason Grade	Total
3	3	≤ 6
3	4	7
4	3	7
4	4	8
4	5	9
5	5	10

#### **5.5.15.** Prior Prostate Cancer History and Therapies

If any of the follow variables have partial dates where only month and year are present, then months will be calculated as ((dose year - parameter year) x12) + ((dose month-parameter month) +1). Otherwise, with full dates, the calculation would be as follows:

Months since last prostate cancer staging = (Dose date – prior prostate cancer staging date)/30.4.

Months from Prior Therapy to Dose =  $(Dose\ Date - Prior\ prostate\ Therapy\ stop\ date)/30.4$ 

Months from Prior Radiation to Dose= (*Dose Date – Prior radiation Therapy stop date*)/30.4

Months from Prior Surgery to Dose =  $(Dose\ Date - Prior\ prostate\ surgery\ date)/30.4$ 

Months from Staging to Dose= (Dose Date – Primary tumor staging date)/30.4

Months since last Prior Therapy to Dose = (Dose Date – Prior therapy date)/30.4.

Full dates must be present for duration variables below:

Duration of Prior Therapy (days) = (Prior Prostate Therapy stop date – Prior prostate therapy start date) +1.

Duration of Prior Radiation Therapy (days) = (Prior Radiation Therapy stop date - Prior Radiation therapy start date) +1

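### SAP 5.5.15 adds one month to history intervals when only month and year are known, which lengthens those values by about 0.9 to 1.0 month on average compared with the full-date rule

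*SAP*

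**What the plan says.** SAP 5.5.15 gives one list of history intervals and two ways to compute them.

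- For variables that "have partial dates where only month and year are present", months are "dose year - parameter year) x12) + ((dose month-parameter month) +1".
- "Otherwise, with full dates, the calculation would be as follows": elapsed days divided by 30.4. Examples are "Months since last prostate cancer staging = (Dose date – prior prostate cancer staging date)/30.4", "Months from Staging to Dose= (Dose Date – Primary tumor staging date)/30.4" and "Months since last Prior Therapy to Dose = (Dose Date – Prior therapy date)/30.4". The radiation formula (counted from "Prior radiation Therapy stop date") and the surgery formula ("Months from Prior Surgery to Dose") have the same shape. None of the six full-date month formulas adds anything.

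The only other +1 in the section is in the two duration formulas, for prior therapy and for prior radiation. These are in days, count both end days, and are computed only from full dates.

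SAP 6.4 plans summary statistics for the time since the latest staging. SAP 6.5 plans a summary of the time since the last surgery. Both are for the safety, evaluable and per-protocol sets.

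**The concern.** The two rules are meant to measure the same quantity, and which one applies depends only on whether the day was recorded. If the rules differ by a constant, subjects with complete dates and subjects with incomplete dates are averaged together with a built-in offset. The summary then reflects date completeness as well as clinical history.

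What is at stake is the accuracy of descriptive baseline rows. The intervals do not enter eligibility, the definition of an analysis set, or a primary or secondary endpoint.

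**Working it through.** The SAP gives formulas here and no numerical result, so there is no stated figure to reproduce. The check applies both formulas to the same pairs of dates.

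**Inputs (all SAP 5.5.15)**

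- Full-date rule: F = (dose date - event date in days) / 30.4
- Partial-date rule: P = 12 × (dose year - event year) + (dose month - event month) + 1
- Excess of the partial-date rule: P - F

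**Worked cases**

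| Event | Dose | Days | F | P | P - F |
|---|---|---|---|---|---|
| 15 Jan (non-leap year) | 15 Mar, same year | 59 | 59/30.4 = 1.94 | 2 + 1 = 3 | +1.06 |
| 14 Mar 2018 | 15 Mar 2018 | 1 | 1/30.4 = 0.03 | 0 + 1 = 1 | +0.97 |
| 15 Mar 2017 | 15 Mar 2018 | 365 | 365/30.4 = 12.01 | 12 + 1 = 13 | +0.99 |
| 28 Feb 2018 | 1 Mar 2018 | 1 | 1/30.4 = 0.03 | 1 + 1 = 2 | +1.97 |
| 1 Mar 2017 | 31 Mar 2018 | 395 | 395/30.4 = 12.99 | 12 + 1 = 13 | +0.01 |

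The last two rows show that the excess for one subject depends on the unrecorded day. It is near 2 when the event falls late in its month and dosing early in its month, and near 0 in the reverse case.

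**Average over unknown days**

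If the event day and the dose day are spread similarly over their months, they cancel on average. The month difference alone then estimates elapsed months. A simulation of 200,000 date pairs per scenario confirms this. The assumptions are dose dates uniform over a two-year window and intervals uniform over the stated range.

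| True interval | Mean P - F, as written | Range of P - F | Mean P - F, +1 removed |
|---|---|---|---|
| 0-60 days | +1.00 | 0.01 to 2.05 | -0.00 |
| 0-1 year | +0.99 | -0.05 to 2.05 | -0.01 |
| 0-10 years | +0.92 | -0.18 to 2.03 | -0.08 |
| 1-10 years | +0.92 | -0.18 to 1.99 | -0.08 |

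As written, the partial-date value is the larger in at least 99.5% of pairs in every scenario. The small negative drift at long intervals comes from the divisor. A mean month is 365.25/12 = 30.44 days, so dividing by 30.4 slightly inflates F. At a mean interval of 59.94 months that is 59.94 × (1 - 30.4/30.4375) = 0.07 month, which accounts for nearly all of the -0.08.

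**Effect on a reported mean**

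The shift is roughly the share of partial dates times 0.92 to 1.00 month. The share is not in the documents, so these values are illustrative:

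- 5%: 0.05 month
- 20%: 0.18 to 0.20 month
- 50%: 0.46 to 0.50 month

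**The case against.** The best defence is that the +1 is an inclusive count of calendar months, which also avoids reporting zero for an event in the month of dosing. The SAP does not say so, and the full-date rule does not follow that convention: it returns 0.03 month for an event the day before dosing. An inclusive count explains the +1 day in the duration formulas. It does not explain a whole month that is added only when the day is missing. The convention may have been intended, but the mismatch remains.

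The objection on materiality stands. A one-month offset is small against a long history: 1/60 = 1.7% of five years and 1/120 = 0.8% of ten. It is noticeable only for short intervals, and the documents do not say how intervals are distributed. SAP 7.4 plans no subgroup analyses, and SAP 10 drops the summaries by prior therapy, so the intervals feed nothing further downstream.

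A reader might also infer more than the documents support:

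- **That every partial date is a month too long.** The offset is an average, and single values run from about -0.2 to +2.0 months.
- **That all four kinds of interval appear in tables.** Only the staging and surgery intervals are named. For therapies, SAP 6.5 names drugs, regimens and types. For radiation, it names prostate relation and site. The table titles in SAP 12.1 do not settle the matter.
- **That the bias differs by cohort or is worse for older records.** This is plausible, but neither document reports date completeness by cohort, variable or age of record.

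**Conclusion.** The inconsistency is real, and no other section corrects or explains it. As written, the partial-date rule lengthens intervals by 0.92 to 1.00 month on average compared with the full-date rule. This rests on the event day being unrelated to the dose day. It changes little across the interval ranges tried.

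The consequence is minor. It is firm for two descriptive baseline rows, the staging and surgery intervals, in three analysis sets. Its size in any table cannot be stated without the share of partial dates. No efficacy conclusion depends on it. It is worth correcting because the direction of the error is known and the repair is nearly free.

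**What to change.** Delete the +1 from the month-and-year-only formula in SAP 5.5.15. Keep +1 in the two duration-in-days formulas, where it counts both end days. The cost is one small text edit and one line of code.

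Deletion removes the average offset, but single values will still be off by about -1.2 to +1.0 months because the day is unknown.

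An alternative is to impute day 15 and divide elapsed days by 30.4 throughout. The day is then wrong by at most 16 days, or 16/30.4 = 0.53 month, and both kinds of date use one formula. It needs a floor at zero: an event in the month of dosing with dosing on the 3rd would otherwise give (3 - 15)/30.4 = -0.39 month.

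With either choice, a table footnote giving the number of partial dates would show how much of each summary rests on the rule.

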#### 5.5.16. Estimate GFR

Estimate GFR (eGFR) will be calculated using the Modification of Diet in Renal Disease (MDRD) Equation:

eGFR (mL/min/1.73 m^2) =  $175 \times (S_{cr})^{-1.154} \times (Age in years)^{-0.203} \times (0.742 if female) \times (1.212 if African American)$ 

Where Scr= Serum creatinine (mg/dL)

#### 5.5.17. Renal impairment

If Estimated GFR  $\geq$ 90 then Normal (no impairment), otherwise if  $0 \leq$ eGFR $\leq$ 90 then Abnormal.

## **5.5.18.** Laboratory Parameter Unit Conversions

Lab Parameter	Original Unit	Conversion Factor (multiply)	Final SI Unit
ALT, Alkaline Phosphatase	U/L	0.0167	Ukat/L
Albumin, Total Protein, hemoglobin	g/dL	10	g/L
BUN	mg/dL	0.357	mmol/L
Calcium	mg/dL	0.25	mmol/L
Chloride, Potassium, Sodium	mEq/L	1	mmol/L
Creatinine	mg/dL	88.4	umol/L
Glucose	mg/dL	0.0555	mmol/L
Total Bilirubin	mg/dL	17.104	umol/L
Total Testosterone	ng/dL	0.0347	nmol/L
Total Testosterone	ng/mL	3.4672	nmol/L
Triglycerides	mg/dL	0.0113	mmol/L
Hematocrit	%	0.01	L/L
Basophils, Eosinophils, lymphocytes, monocytes, neutrophils, platelets, WBC count	k/cumm	1	10  /L
Basophils, Eosinophils, lymphocytes, monocytes, neutrophils, platelets, WBC count	k/μL	1	10  /L
Basophils, Eosinophils, lymphocytes, monocytes, neutrophils, platelets, WBC count	$10^3/\mu$ L	1	10  /L
Basophils, Eosinophils, lymphocytes, monocytes, neutrophils, platelets, WBC count	10  /L	1	10  /L

Basophils, Eosinophils, lymphocytes, monocytes, neutrophils, platelets, WBC count	k/mcl	1	10  /L
RBC Count	m/mcl	1	$10^{12}/L$
RBC Count	m/µL	1	$10^{12}/L$
RBC Count	mil/cumm	1	$10^{12}/L$
RBC Count	10  /L	1	$10^{12}/L$
RBC Count	$10^{12}/L$	1	$10^{12}/L$
RBC Count	$10^6/\mu L$	1	$10^{12}/L$
PSA	ng/mL	1	ug/L

## 5.6. Handling of Missing Data

### **5.6.1.** Missing Efficacy Endpoints

No imputation methods will be employed.

## 5.6.2. Missing Start and Stop Dates for Concomitant Medication

Partial or missing medication start, and end dates will be categorized as occurring prior to or after dose using the following logic. If a medication categorized as post-dose had a start date< dose date or a start year <dose year or a start year=dose year and start month<dose month then it will be summarized as both a pre- and post- medication.

Start Date	Stop Date	Category
< dose date or Year< dose year or year= dose year and	date< dose date or year <dose and<="" or="" td="" year="">Pre-dose	</dose>	Pre-dose
month< dose month or	month <dose month<="" td="">	</dose>	
year=dose year or date=missing		
< dose date or Year< dose year or year= dose year and	Missing or date< dose date or year <dose or="" year="dose</td">Pre-Dose	</dose>	Pre-Dose
month< dose month	year and month <dose month="" or="" td="" year="dose" year<="">	</dose>	
Year = dose year and month = dose month and day is	Year = dose year and month < dose month	Pre-dose
missing  >dose date or year=dose year and month≥ dose month	missing	Post Dose
>dose date or year=dose year and month> dose month		Post Dose
	≥ dose date or year>dose year or year=dose year and month ≥ dose month	Post Dose
Date <dose and="" date="" dose="" month<="" month≤dose="" or="" td="" year="" ≤="">Year=dose year and month=dose month	Post Dose	</dose>	Year=dose year and month=dose month	Post Dose
Missing	missing	Post Dose
< dose date or Year< dose	≥ dose date or year>dose year	Pre and Post Dose
year or year= dose year and	or year=dose year and month ≥	
month< dose month	dose month	

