## 3.3. Safety Endpoints

- 1. Treatment-emergent adverse events (TEAEs) and SAEs
- 2. Change from baseline in clinical laboratory parameters
- 3. Change from baseline in ECGs
- 4. Change from baseline in vital signs
- 5. Concomitant medication use

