#### **5.5.5.** Prior and Concomitant Medications

Prior medications are those administered prior to F-DCFPyL administration date; concomitant medications are those administered from F-DCFPyL administration through last study visit. If the concomitant medication does not have a full date then the algorithm in Section 5.6.2 will be used to determine if it is a pre- or post-dose medication.

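### SAP 5.6.2 classes a drug started before dosing with a missing stop date as pre-dose only, against the SAP's own definition of concomitant medication

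*SAP*

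**What the plan says.** SAP 3.3 lists "Concomitant medication use" among the safety endpoints. SAP 8.3 tabulates it by frequency and percentage in the safety set (Table 14.3.6-6).

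SAP 5.5.5 gives the definition: "concomitant medications are those administered from" tracer administration through the last study visit. It then hands incomplete records to the date table: "If the concomitant medication does not have a full date then the algorithm in Section 5.6.2 will be used".

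Three rules in SAP 5.6.2 matter here:

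- **Row 2.** The start cell opens "< dose date or Year< dose year or year= dose year and" and goes on to an earlier month, so it covers any start known to precede dosing. The stop cell opens "Missing or date< dose date or year". The category is Pre-Dose.
- **Last row.** The category is "Pre and Post Dose". It needs a start before dosing and a recorded stop, full or partial, on or after dosing.
- **Sentence above the table.** It adds a second label to some drugs, and it begins "If a medication categorized as post-dose had a start date< dose date or a start year <dose year". It reaches only drugs that the table has already placed in the post-dose class.

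**The concern.** A missing stop date is compatible with a drug that ended years ago and with one still being taken on the imaging day. Row 2 settles that uncertainty as stopped before dosing, without evidence. The rest of the table tends the other way: with both dates missing, the drug counts as Post Dose. So knowing that a drug began before dosing, and knowing nothing of its end, removes it from the concomitant class, whereas knowing nothing at all keeps it in.

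What is at stake is whether the concomitant-medication table shows what subjects were taking at and after dosing. If a blank stop date is how an ongoing drug is recorded, long-standing medication is the group most exposed.

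**Working it through.** The plan gives no figure to reproduce. The check applies the nine rows of SAP 5.6.2 to test records. The dose date of 15 June 2017 is hypothetical. Some cells are damaged in the copy reviewed and were read in their evident sense. Month and year tests were applied only to partial dates.

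| Start | Stop | Row met | Result |
|---|---|---|---|
| 1 Mar 2015 | missing | 2 | Pre-Dose only |
| 14 Jun 2017 | missing | 2 | Pre-Dose only |
| 2016, no month | missing | 2 | Pre-Dose only |
| 1 Mar 2015 | 2017, no month | 2 | Pre-Dose only |
| 1 Mar 2015 | Jun 2017, no day | 7 and 9 | both |
| 1 Mar 2015 | 1 Jul 2017 | 9 | both |
| missing | missing | 8 | Post Dose |

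**Can another rule bring the row 2 drugs back?** Row 9 cannot, because it needs a recorded stop. The sentence above the table cannot, because it starts from drugs already classed post-dose. Rows 4 and 5, on this reading, need a start after dosing, or a partial start in the dosing month or later. So for the first three records Pre-Dose is final.

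**Is row 2 consistent with the rest?** A stop known only to the dosing month (row 7) is resolved inclusively: Post Dose, then both through the introductory sentence. A stop known only to the dosing year is less precise, yet row 2 resolves it as ended before dosing. This fourth record rests on the damaged end of the row 2 stop cell and is less certain than the first three, where the words for a missing stop and the Pre-Dose category are legible in one row.

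**A start earlier in the dosing month.** Take dosing on 20 March 2017, a start on 3 March 2017 and a missing stop.

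- If month tests apply only to partial dates, 3 March is before 20 March. Only row 2 is met, and the result is Pre-Dose.
- If the month test in row 4 is also applied to full dates, month 3 is not below month 3, so row 4 is met as well and gives Post Dose. The introductory sentence would then make the drug both.

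The SAP does not say which reading holds, so two programmers could class the record differently.

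**Records with no row.** With month tests kept to partial dates, a start on the dose date itself with a missing stop meets no row. Nor does a start known only to the dosing year with a missing stop. This bears on the wording of the fix.

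**The case against.** The strongest reply is that little is lost in practice.

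- **The drugs are still reported.** A reader might infer that they vanish from the study report. They do not. SAP 6.6 covers prior medications and medications present at entry, and Table 14.1.1-7 shows baseline medication use in the safety set. What stands is that they would be absent from the concomitant table.
- **The data capture is unseen.** A reader might infer that every ongoing drug begun before dosing is dropped. That needs ongoing drugs to be held with a blank stop date and no flag applied first. Neither document describes the medication page of the eCRF. A flag used before the table would remove the problem, but the SAP states no such step.
- **The overlap between rows is not certain.** It appears only if month tests are applied to full dates, which is not the natural reading of a table for partial dates. It stands as an ambiguity, not as a demonstrated double classification.
- **Cancer therapy in Cohort B.** A reader might infer that ongoing systemic treatment would be hidden. The documents do not support that. Past and present prostate cancer therapies are collected in the prostate history (Protocol 11.1.1), and prior therapies are tabulated separately (SAP 6.5, Table 14.1.1-4).
- **The table is descriptive.** SAP 8.3 plans no test on it, and the protocol's own safety endpoints (5.2) do not name concomitant medication. That limits the importance of the point but does not make the rule right.

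None of this answers the conflict between row 2 and SAP 5.5.5.

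**Conclusion.** The rule is wrong as written. A start before dosing with a missing stop is classed Pre-Dose only, which contradicts the definition in SAP 5.5.5 and the table's handling of records with both dates missing. The same appears true for a stop known only as the dose year, as far as the damaged cell can be read.

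The effect is conditional and one-sided. If ongoing drugs carry a blank stop date, Table 14.3.6-6 understates concomitant use by all those begun before dosing, apart from any starts in the dosing month that a program also reads into row 4. If an ongoing flag is applied first, the loss for ongoing drugs is nil. The documents give no medication counts or rate of missing stop dates, so no figure between these can be supported.

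Sensitivity, specificity and the definition of treatment-emergent events do not use this classification. The point is worth correcting because it concerns a listed SAP safety endpoint and the correction is cheap.

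**What to change.** In SAP 5.6.2, row 2:

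1. Assign the category "Pre and Post Dose" when the start precedes dosing and the stop is missing, marked ongoing, or partial and could fall on or after the dose date.
2. Keep Pre-Dose only when the known part of the stop date shows that the drug ended before dosing.
3. State that full dates are compared first, and that month and year tests are used only where the day or month is missing. This settles the start earlier in the dosing month.
4. With that order in place, give an explicit category to the two patterns that otherwise meet no row: a start on the dose date, or known only to the dosing year, with a missing stop.
5. State how an ongoing medication is recorded and that it is handled under item 1. If the eCRF already has a flag, one sentence saying so is enough.

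The cost is an edit to one table and its program. The downside is that some drugs that really stopped before dosing, with no stop date recorded, will be counted as concomitant. That is the direction the table already takes when both dates are missing.

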#### 6. STUDY POPULATION

## 6.1. Disposition

Subject disposition will display the number of consented subjects and the percentage of them who failed screening. The number of subjects in the safety analysis set as well as the number and percentage of subjects in the evaluable set, per-protocol set, change in planned protocol procedure set, and PK sets will also be summarized. The number and percentage of subjects who completed or discontinued from the study with the reason for discontinuation, will be tabulated. All percentages for discontinuation reasons will be based on the number of subjects in the safety population.

#### **6.2.** Protocol Deviations

Protocol deviations will be summarized in the clinical study report based on the protocol deviation log.

Protocol deviations will be listed, including their classification as major or minor for the Safety Set.

## 6.3. Demographic and Baseline Characteristics

Demographic and baseline characteristics: age at informed consent in years, categorical age (<65 years, ≥65 years), race, ethnicity, height in cm, weight in kg, and BMI in kg/m² will be summarized by cohort for the safety set, the evaluable set, and the per protocol set.

## 6.4. Medical History, including Prostate Cancer History

Medical history will be summarized by MedDRA system organ class (SOC) and preferred term (PT) using frequencies and percentages.

Prior prostate cancer history will also be summarized using summary statistics for months since most recent prostate cancer staging, PSA (ng/mL) and testosterone (ng/dL). Frequencies and percentages will be presented for whether PSA results were captured within 30 days from Baseline, PSA groups, primary Gleason grade, secondary Gleason grade, Gleason total score, primary tumor stage (T), regional lymph node stage (N), distant metastasis stage (M) and renal impairment status.

Medical history and prostate cancer history will be presented for the safety set, the evaluable set and the per-protocol set.

